8.2 STATISTICAL ANALYSES

Due to the nature of the study data, descriptive statistics will be used to summarize all endpoints. Tests for subgroup analyses are purely explorative.

8.2.1 Safety Analyses

Treatment-emergent adverse events are adverse events which worsen or start after start of treatment with abrocitinib but no later than 28 days after end of treatment with abrocitinib.

In addition to the analysis of treatment-emergent adverse events and drug-related adverse events as specified in 6.2 adverse events which occurred under another systemic treatment, following cessation of abrocitinib, will be given and presented in a separated listing. Number and percentage of SOC and PT will be presented according to maximal grade.

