For each patient, the safety event reporting period begins at the time of the patient's informed consent, which is obtained prior to the patient's enrollment in the study and lasts through the end of the observation period of the study; a report must be submitted to Pfizer Safety (or its designated representative) for any of the types of safety events listed in the table above occurring during this period. Most often, the date of informed consent is the same as the date of enrollment. In some situations, there may be a lag between the dates of informed consent and enrollment. In these instances, if a patient provides informed consent but is never enrolled in the study (eg, patient changes his/her mind about participation), the reporting period ends on the date of the decision to not enroll the patient. If the investigator becomes aware of a SAE occurring at any time after completion of the study and s/he considers the serious AE to be related to a Pfizer product, the SAE also must be reported to Pfizer Safety.

Causality assessment

The investigator is required to assess and record the causal relationship. For all AEs, sufficient information should be obtained by the investigator to determine the causality of each AE. For AEs with a causal relationship to abrocitinib, follow-up by the investigator is required until the event and/or its sequelae resolve or stabilize at a level acceptable to the investigator, and Pfizer concurs with that assessment.

An investigator's causality assessment is the determination of whether there exists a reasonable possibility that abrocitinib caused or contributed to an AE. If the investigator's final determination of causality is "unknown" and s/he cannot determine whether abrocitinib caused the event, the safety event must be reported within 24 hours.

If the investigator cannot determine the etiology of the event but s/he determines that abrocitinib did not cause the event, this should be clearly documented on the eCRF and in case of technical difficulties only, this also applies to the NIS AEM Report Form.

DEFINITIONS OF SAFETY EVENTS

Adverse events

An AE is any untoward medical occurrence in a patient administered a medicinal product. The event need not necessarily have a causal relationship with the product treatment or usage. Examples of AEs include but are not limited to:

• Abnormal test findings (see below for circumstances in which an abnormal test finding constitutes an AE);

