EASI	X	X	X	X	X	X

Study period based on routine visits	Baseline (Enroll ment)	Month 1	Month 3	Month 6	Month 9	Month 12 End of Study (EoS)
IGA	X	X	X	X	X	X
Pruritus-NRS	X	X	X	X	X	X
PP-NRS	X	X	X	X	X	X
DLQI	X	X	X	X	X	X
POEM	X	X	X	X	X	X
MOS	X	X	X	X	X	X
PBI	X	X	X	X	X	X
EQ-5D-5L	X	X	X	X	X	X
HADS	X	X	X	X	X	X

^{*} This includes patients who discontinued treatment with abrocitinib.

Figure 1. Timelines

The planned observation period of each patient is 12 months. In this time period up to 6 visits will be documented.

Figure 2. Study Period

Table 2. Definition of time windows for study visits

In order to collect comparable study data, Visits 1 to 3 occurring ± 14 days and Visits 4 to 6 occurring ± 28 days of the scheduled visit date will be used for data analysis (interim analysis).

Visit Label	Target Day	Definition [Day window]
Enrolment	1	1
Month 1	30	16 to 44
Month 3	91	77 to 105
Month 6	182	154 to 210
Month 9	273	245 to 301
Month 12	365	337 to 393

Visits that do not meet the defined windows as displayed in the table above will also be included in the final analysis and clinical study report. Therefore, all visits will be included using the visit time slots shown below. If more than one visit appears in a 3-month window, only the visit closest to the target day will be respected.

Amended definition:

Visit designation	Target Day	Definition [Day window]
Enrolment	1	1
Month 1	30	2 to 44
Month 3	91	45 to 105
Month 6	182	106 to 210
Month 9	273	211 to 301
Month 12	365	302 to 393

However, for analysis of safety parameters, all AEs/SAEs documented within the applicable reporting period will be analyzed.

- For the lab values, if the calculated study day for the labelled baseline visit is not study Day 1, but falls within 40 days before the start of the study dosing, then that data should be used for the baseline instead of leaving baseline missing.
- For the other values, if the calculated study day for the labelled baseline visit is not study Day 1, but falls before the start of the study dosing, then that data should be used for the baseline instead of leaving baseline missing.
- If baseline is missing there will be no imputation and although the subject's data will be included in summary data it will not be included in any change from baseline analyses.

If two or more routine visits fall into the same window, keep the one closest to the Target Day. If two routine visits are equal distance from the Target Day in absolute value, the later visit should be used.

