6.2 SAFETY ENDPOINTS

Incidence and severity of all adverse events including serious adverse events (SAEs). The reporting of safety data will be in accordance with Pfizer Data Standards.

Variable	Role	Data source(s)	Operational definition
Occurrence of adverse events	Safety outcome	Case records	Number and percentage of SOC and PT according to maximal grade of adverse event (patient based)
Occurrence of adverse drug reactions	Safety outcome	Case records	Number and percentage of SOC and PT according to maximal grade of adverse drug reaction (patient based)
Occurrence of serious adverse events	Safety outcome	Case records	Number and percentage of SOC and PT according to maximal grade of serious adverse event (patient based)
Occurrence of serious adverse drug reactions Safety outcome		Case records	Number and percentage of SOC and PT according to maximal grade of serious adverse drug reaction (patient based)
Reason for seriousness	Safety outcome	Case records	Number and percentage for each reason (event based)
Occurrence of scenarios involving drug exposure Safety outcome		Case records	Number and percentage (patient based)
Reason for scenario involving drug exposure	Safety outcome	Case records	Number and percentage for each reason (event based)
Worst outcome	Safety outcome	Case records	Number and percentage (patient based), order: recovered,

			recovered with sequelae, not recovered, unknown, fatal
Action taken	Safety outcome	Case records	Number and percentage for each reason (event based)
Type and results of performed laboratory checks	Potential confounder, potential subgroup identifier, safety outcome	Case records	Summary statistics (n, mean, median, standard deviation, minimum and maximum) of the minimal and maximal value per patient, respectively

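### SAP 8.2.1 conflicts with SAP 6.2, SAP 1.1 and Protocol 9.7 on whether the adverse-event tables hold all reported events or only treatment-emergent and drug-related ones

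*SAP*

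**What the plan says.** Four places bear on which adverse events (AEs) and serious adverse events (SAEs) are reported.

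- **SAP 8.2.1** sets the treatment-emergent window: "adverse events which worsen or start after start of treatment with abrocitinib but no later than 28 days after end of treatment with abrocitinib". It then introduces a further output with the words "In addition to the analysis of treatment-emergent adverse events and drug-related adverse events as specified in 6.2", so it describes the 6.2 analyses as those two kinds of event. The further output is that "adverse events which occurred under another systemic treatment, following cessation of abrocitinib, will be given and presented in a separated listing", with counts by system organ class and preferred term.
- **SAP 6.2** opens with a wider scope: "Incidence and severity of all adverse events including serious adverse events (SAEs". Its table rows for AEs and SAEs carry no time limit and no relatedness condition. The term treatment-emergent does not occur there.
- **SAP 1.1 and Protocol 9.7**, in the text on visit windows, both state that "for analysis of safety parameters, all AEs/SAEs documented within the applicable reporting period will be analyzed".
- **Protocol 11** starts the reporting period at informed consent and says that it "lasts through the end of the observation period of the study". Under Protocol 7.4 and 10.3, stopping abrocitinib is not withdrawal, and patients are to be followed for 12 months whatever their treatment status.

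The note closing SAP 8.2.3 says that the 6.2 endpoints are analysed for the safety set, which is every consenting patient with at least one dose. SAP 9 places the table shells in a separate mock-up document.

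**The concern.** The plan deliberately keeps collecting safety data after abrocitinib is stopped, so the rule for reporting those data has to be unambiguous. It is not. A programmer who takes 8.2.1 as the specification would filter the AE and SAE tables to treatment-emergent and drug-related events. One who takes 6.2 as the specification would apply no filter.

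The two choices give different safety reports. With the filter, some collected events, including serious ones, would be left out of the outputs that 8.2.1 names, contrary to the commitment in SAP 1.1 and Protocol 9.7. Without it, nothing is lost, but the incidence tables mix events on abrocitinib, events off all systemic treatment and events on a successor drug, with no split by exposure. In a single-arm study with safety among its objectives, a reader of the report needs to know which of these a percentage describes.

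**Working it through.** The plan states no figure to reproduce. There are two checks.

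**Coverage.** Classify each AE by three yes/no attributes: treatment-emergent, drug-related, and occurring under another systemic treatment after abrocitinib. This gives 2 × 2 × 2 = 8 kinds of event.

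- Under 8.2.1, an event is in a named output if at least one attribute is yes. That covers 7 of 8 kinds. The one left over is not treatment-emergent, not drug-related and not under another systemic drug.
- Under 6.2 and 1.1 as worded, no attribute matters, so all 8 of 8 are covered.

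Two groups fall in the uncovered cell:

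1. Unrelated events starting more than 28 days after the last dose in a patient who is on no other systemic drug.
2. Unrelated events between consent and first dose that do not worsen on treatment, because the reporting period opens at consent and the treatment-emergent window opens at treatment start.

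There is also an overlap. An event within 28 days of stopping, but after the next systemic drug was started, is both treatment-emergent and in the separate listing.

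**Length of follow-up outside the window.** Inputs: the 28 days from SAP 8.2.1, and the Month 12 target day 365 and upper window limit 393 from the visit-window tables. The stop days are assumed; the first four are the visit target days.

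Days outside the window = max(0, end of observation − (stop day + 28)).

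| Assumed stop day | Window closes | Days left, observation to day 365 | Days left, observation to day 393 |
|---|---|---|---|
| 30 | 58 | 307 (307/365 = 84.1%) | 335 |
| 91 | 119 | 246 (246/365 = 67.4%) | 274 |
| 182 | 210 | 155 (155/365 = 42.5%) | 183 |
| 273 | 301 | 64 (64/365 = 17.5%) | 92 |
| 337 | 365 | 0 | 28 |
| 365 | 393 | 0 | 0 |

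For a patient who starts no other systemic drug, only drug-related events in those remaining days would reach an output named in 8.2.1.

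**The case against.** The strongest reply is that nothing is lost. Section 6.2 is the operative specification: its rows are unfiltered, 8.2.3 applies it to the whole safety set, and SAP 1.1 and Protocol 9.7 agree with it. Section 8.2.1 refers back to 6.2, adds a listing, and never says that other events are excluded. This stands to the extent that omission is not established. A reader might infer from 8.2.1 that late, unrelated events appear in no safety output at all; the documents do not support that, because 6.2 as worded includes them.

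The reply does not remove the conflict. The definition of treatment-emergent in 8.2.1 has no evident use unless it restricts the 6.2 tables. Presenting successor-drug events in addition to 6.2 also suggests that they are not already there. Both readings are tenable.

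A second reply is that attribution is already handled: successor-drug events have their own listing with counts, adverse drug reactions have their own tables, and causality is recorded for every AE. This is largely fair, and an event appearing in both a table and a supplementary listing is not an error. What remains is that the all-event tables, read literally, have no split by exposure period.

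A third reply is that crude percentages are a legitimate summary in a descriptive study. I agree. Exposure-adjusted rates are a reporting preference and not part of this point.

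**Conclusion.** The finding is an internal inconsistency on the scope of the AE and SAE tables, with a real but not certain risk of omission. It should be corrected, because it changes which events are reported and under which exposure. It is more than a missing detail.

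The size depends on when patients stop. On the filtered reading, with observation ending on day 365, the days outside the treatment-emergent window run from 307 for a stop on day 30 to none for a stop on day 337 or later. These figures assume follow-up to the stated end, whereas no visit is mandatory and patients who stop treatment may, but need not, stay under observation. The length of the interval from consent to first dose is not given; Protocol 11 says that consent and enrolment most often share a date.

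Two further inferences are tempting and should not be drawn. One is a total of unreported patient-years, or a figure for how far the crude incidence understates risk; the documents give no discontinuation rate, no stop-day distribution and no share of patients moving to another systemic drug. The other is that late malignancies or cardiovascular events are a designated safety focus; the documents name these as comorbidities of interest, not as safety events of interest.

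The mock-up document may already settle which reading applies, but it could not be examined.

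**What to change.** Amend SAP 6.2 and 8.2.1 so that they agree with each other, with SAP 1.1 and with Protocol 9.7. State that all AEs and SAEs in the reporting period are tabulated overall, and also by exclusive period, assigned by date of onset or worsening:

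- **(0)** consent to before first dose;
- **(a)** first dose to 28 days after last dose, which is the existing treatment-emergent definition including its worsening limb, with a flag for events after another systemic drug was started;
- **(b)** more than 28 days after last dose, after another systemic treatment was started;
- **(c)** more than 28 days after last dose, with no other systemic treatment started.

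Use the patients who entered each period as its denominator; a patient may pass from (c) to (b). Exposure-adjusted rates are optional.

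The split between (b) and (c) depends on whether another systemic drug has been started, so it needs no stop date for that drug. Protocol 9.2.4.5 already collects the abrocitinib stop date and the start date of the new treatment. Protocol Table 2 lists the date of initiation, and the treatment-emergent definition already presupposes a date of onset or worsening. No new data collection is needed.

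The cost is SAP wording, matching changes to the table shells before database lock, and longer tables.

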8.2.2 Analyses of endpoints

Please refer to the "operational definition" in section 6.1 and 6.3.

8.2.3 Summary of Analyses

Outcome	Analysis Set	Supports Protocol Objective Number	Subgroups	Statistical Method	Covariates/ Strata	Missing Data
Response based on achieving the IGA of clear (0) or almost clear (1) (on a 5-point scale) at month 3	FAS, mFAS, PP	1	All	Percentage of patients with IGA score 0 or 1 at month 3 Chi-Square test respective Fisher's exact test for subgroups	None	Excluded
Response based on achieving the EASI-75 at month 3	FAS, mFAS, PP	2	All	Percentage of patients with 75% reduction from baseline in EASI at month 3 Chi-Square test respective Fisher's exact test for subgroups	None	Excluded
Response based on achieving the IGA of clear (0) or almost clear (1) (on a 5-point scale)	FAS, mFAS, PP	3	All	Percentage of patients with IGA score 0 or 1 irrespective of the point in time Chi-Square test respective Fisher's exact test for subgroups	None	Excluded
Response based on achieving the EASI-75	FAS, mFAS, PP	4	All	Percentage of patients with 75% reduction from baseline in EASI irrespective of the point in time Chi-Square test respective Fisher's exact test for subgroups	None	Excluded

Outcome **Analysis Set Supports Missing Data** Subgroups Statistical Method Covariates/ Strata Protocol **Objective** Number Response based on FAS, mFAS, PP All Percentage of patients None Excluded achieving the EASI-90 with 90% reduction from baseline in EASI irrespective of the 5 point in time Chi-Square test respective Fisher's exact test for subgroups Percentage of patients Response based on FAS, mFAS, PP Excluded All None achieving the IGA of with IGA score 0 or 1 clear (0) or almost clear and a reduction from (1) and a reduction from baseline of ≥ 2 points baseline of ≥2 points irrespective of the 6 point in time Chi-Square test respective Fisher's exact test for subgroups Percentage change of FAS, mFAS, PP (score at respective All None Excluded IGA compared to visit - score at baseline baseline)/score at 7 baseline*100 Mann-Whitney-U test for subgroups (score at respective Percentage change of FAS, mFAS, PP All None Excluded SCORAD compared to visit - score at baseline baseline)/score at baseline*100 Mann-Whitney-U test for subgroups Absolute EASI values FAS, mFAS, PP All Summary statistics (n, None Excluded mean, median, over time standard deviation, 9 minimum and maximum) of the score at each point in time

Outcome **Analysis Set Supports Missing Data** Subgroups Statistical Method Covariates/ Strata Protocol **Objective** Number Mann-Whitney-U test for subgroups Percentage change of FAS, mFAS, PP A11 (score at respective None Excluded EASI compared to visit - score at baseline baseline)/score at 10 baseline*100 Mann-Whitney-U test for subgroups Absolute change of IGA FAS, mFAS, PP All Summary statistics (n, None Excluded compared to baseline mean, median, standard deviation, minimum and 11 maximum) of the score at each point in time Mann-Whitney-U test for subgroups Response based on FAS, mFAS, PP All Percentage of patients None Excluded achieving at least 4 achieving at least 4 points improvement of points improvement of Pruritus NRS from Pruritus NRS from baseline and patients baseline Percentage of patients with Pruritus NRS ≤1 13 with Pruritus NRS <1 Chi-Square test respective Fisher's exact test for subgroups Response based on FAS, mFAS, PP Percentage of patients All None Excluded achieving at least 4 achieving at least 4 points improvement of points improvement of PP NRS from baseline PP NRS from baseline and patients with PP Percentage of patients 14 NRS ≤1 with PP NRS ≤1 Chi-Square test respective Fisher's exact test for subgroups

Outcome **Analysis Set Supports** Covariates/ Strata **Missing Data** Subgroups Statistical Method Protocol **Objective** Number Change of Peak-Pruritus FAS, mFAS, PP All (score at respective None Excluded NRS over time visit - score at baseline)/score at 15 baseline*100 Mann-Whitney-U test for subgroups (score at respective Change of POEM from FAS, mFAS, PP A11 None Excluded visit - score at baseline baseline)/score at 15 baseline*100 Mann-Whitney-U test for subgroups Change of MOS from FAS, mFAS, PP All (score at respective None Excluded baseline visit - score at baseline)/score at 17 baseline*100 Mann-Whitney-U test for subgroups Response based on FAS, mFAS, PP All Percentage of patients None Excluded achieving at least 4 achieving at least 4 points improvement of points improvement of DLQI from baseline and DLOI from baseline patients with DLQI ≤1 Percentage of patients 18 with DLQI ≤1 Chi-Square test respective Fisher's exact test for subgroups Change of DLQI from FAS, mFAS, PP All (score at respective None Excluded baseline visit - score at baseline)/score at 19 baseline*100 Mann-Whitney-U test for subgroups Change of HADS from FAS, mFAS, PP All (score at respective None Excluded 20 baseline visit - score at

Outcome **Analysis Set Supports Missing Data** Subgroups Statistical Method Covariates/ Strata Protocol **Objective** Number baseline)/score at baseline*100 Mann-Whitney-U test for subgroups Change of EuroQol five-(score at respective FAS, mFAS, PP All None Excluded dimensional-five level visit - score at (EQ-5D-5L) from baseline)/score at 21 baseline baseline*100 Mann-Whitney-U test for subgroups Change of PBI from FAS, mFAS, PP All (score at respective None Excluded visit - score at baseline baseline)/score at 22 baseline*100 Mann-Whitney-U test for subgroups Patient's satisfaction FAS, mFAS, PP All Frequency tables for None Excluded satisfaction with with treatment (PBI after baseline) effectiveness and tolerability 23 Chi-Square test respective Fisher's exact test for subgroups Number of days with FAS, mFAS, PP All Excluded Summary statistics (n, None topical-treatment use mean, median, standard deviation, (TCS, TCI) 24 minimum and maximum) Mann-Whitney-U test for subgroups Number of days with FAS, mFAS, PP All Summary statistics (n, None Excluded emollients use mean, median, standard deviation, 25 minimum and maximum)

Outcome	Analysis Set	Supports Protocol Objective Number	Subgroups	Statistical Method	Covariates/ Strata	Missing Data
				Mann-Whitney-U test for subgroups		
AD-treatment with abrocitinib and/or without topicals – total days	FAS, mFAS, PP	26	All	Summary statistics (n, mean, median, standard deviation, minimum and maximum) Mann-Whitney-U test for subgroups	None	Excluded
AD-treatment with abrocitinib and/or without topicals – stratified by abrocitinib dose	FAS, mFAS, PP	27	All	Summary statistics (n, mean, median, standard deviation, minimum and maximum) Mann-Whitney-U test for subgroups	None	Excluded
Number of flares	FAS, mFAS, PP	28	All	Summary statistics (n, mean, median, standard deviation, minimum and maximum) Mann-Whitney-U test for subgroups	None	Excluded

All explorative endpoints mentioned in section 6.3 will be analyzed for FAS and all subgroups, respectively. Safety enpoints, as given in section 6.2 will be analyzed for SAF.

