9.1.1. Endpoints

Primary Endpoints:

- a. Response based on achieving the **IGA** of clear (0) or almost clear (1) (on a 5-point scale) at month 3.
- b. Response based on achieving the **EASI-75** at month 3.

Secondary Endpoints:

Physician's global assessment of efficacy parameters (assessed at all visits [except for month 3 for a. and b.]):

- a. Response based on achieving the **IGA** of clear (0) or almost clear (1) (on a 5-point scale).
- b. Percentage of patients with EASI-75 response compared to baseline.
- c. Response based on achieving the EASI-90.
- d. Response based on achieving the **IGA** of clear (0) or almost clear (1) and a reduction from baseline of ≥ 2 points.
- e. Percentage change of **IGA** compared to baseline.
- f. Percentage change of **SCORAD** compared to baseline.
- g. Absolute **EASI** values over time.
- h. Percentage change of EASI compared to baseline.
- i. Absolute change of **IGA** compared to baseline.

Patient's assessment of efficacy and quality parameters (assessed at all visits):

- a. Response based on achieving at least 4 points improvement of Pruritus **NRS** from baseline.
- b. Change of Peak-Pruritus NRS over time.
- c. Change of **POEM** from baseline.
- d. Change of MOS from baseline.
- e. Change of DLQI from baseline.

- f. Change of HADS from baseline.
- g. Change of EuroQol five-dimensional-five level (EQ-5D-5L) from baseline.
- h. Patient's satisfaction with treatment measured by PBI.
- i. Patient's expectation of treatment measured as PBI at baseline.
- j. Number of days with topical-treatment use (TCS, TCI).
- k. Number of days with emollients use.

Explorative Endpoints:

Treatment characteristics (assessed at all visits):

- a. Concomitant treatments.
- b. Tolerability of abrocitinib and reasons for discontinuation.
- c. Dosage of abrocitinib.
- d. Compliance with abrocitinib treatment.

Patient characteristics assessed at baseline visit only (except for c., f., g., and h. with additional assessment at subsequent visits):

- a. Demographic data of patient (age, sex, weight, occupation, alcohol/smoking, family history).
- b. Clinical history of AD treatment before non-interventional study start.

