1.3 STUDY OBJECTIVES

The objectives of this non-interventional study are to examine patient characteristics, usage and effectiveness of abrocitinib in adult patients with moderate to severe AD who have been chosen to start treatment with abrocitinib in a real-world context such as dermatological practices in Germany. The following factors will be considered, if collected as part of the medical routine:

Primary Objective:

The primary objective of this non-interventional study is to describe the efficacy of abrocitinib treatment.

- In terms of patients achieving a clear or almost clear AD morphology 3 months after first prescription of abrocitinib based on the IGA Questionnaire.
- In terms of patients achieving $a \ge 75\%$ improvement in lesion extent and severity 3 months after first prescription of abrocitinib based on the EASI.

Secondary Objectives:

The secondary objectives of this non-interventional study are:

• To document the efficacy of abrocitinib treatment based on physicians'

- assessment:
 Physician's global assessment of AD: Scoring Atopic Dermatitis (SCORAD), EASI, IGA change to baseline.
- To document the efficacy of abrocitinib treatment based on patients' assessment:
 - Patient's global assessment of AD: change in quality of life, Dermatology Life Quality-Index (DLQI), Patient Oriented Eczema Measure (POEM);
 - Patient's assessment of anxiety and depression: Hospital Anxiety and Depression Scale (HADS);
 - Patient's assessment of pruritus: Peak Pruritus Numeric Rating Scale (PP-NRS), mean-NRS and sleep: Medical Outcomes Study Sleep (MOS) Scale;
 - Meeting the patient's expectations (change in the Patient Benefit Index [PBI]) with regard to medical treatment;
 - Number of days with topical-treatment use (topical corticosteroid (TCS), topical calcineurin inhibitor (TCI);
 - Number of days with emollients use.

Explorative objectives:

The explorative objectives of this non-interventional study are:

- *To document patient characteristics and treatment decisions in terms of:*
 - patient characteristics, clinical history, comorbidities and previous therapies;
 - o reasons for starting/ending treatment with abrocitinib, concomitant treatments;
 - o dosage and actual use of abrocitinib as assessed by the treating physician and the patient.

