6.1 EFFICACY/EFFECTIVENESS ENDPOINT(S)

Effectiveness endpoints comprise of all primary and secondary endpoints, i.e. effectiveness, and quality parameters assessed by the physicians and the patients.

Primary endpoint analysis

Variable	Role	Data source(s)	Operational definition
EASI	Primary outcome variable	Case records	Percentage of patients with 75% reduction from baseline in EASI at month 3
IGA	Primary outcome variable	Case records	Percentage of patients with IGA score 0 or 1 at month 3

Secondary endpoint analysis

Variable	Role	Data source(s)	Operational definition
SCORAD	Secondary outcome variable	Case records	Summary statistics (n, mean, median, standard deviation, minimum and maximum) of the total score and SCORAD-A at each point in time, respectively as well as the respective percentage change to baseline
EASI	Secondary outcome variable	Case records	 Percentage of patients with 75% reduction from baseline in EASI irrespective of the point in time Percentage of patients with 90% reduction from baseline in EASI irrespective of the point in time Summary statistics (n, mean, median, standard deviation, minimum and maximum) of the score at each point in time as well as the respective percentage change to baseline
IGA	Secondary outcome variable	Case records	 Percentage of patients with IGA score 0 or 1 irrespective of the point in time Percentage of patients with IGA score 0 or 1 and a reduction from baseline of ≥2 points irrespective of the point in time Summary statistics (n, mean, median, standard deviation, minimum and maximum) of the score at each point in time as well as the respective percentage change to baseline ((score at respective visit – score at baseline)/score at baseline*100)

Pruritus- NRS	Secondary outcome variable	Case records	Percentage of patients achieving at least 4 points improvement of Pruritus NRS from baseline Summary statistics (n, mean, median, standard deviation, minimum and maximum) of the score at each point in time as well as the percentage change to baseline Percentage of patients with Pruritus NRS ≤1
PP- NRS	Secondary outcome variable	Case records	 Percentage of patients achieving at least 4 points improvement of PP NRS from baseline Summary statistics (n, mean, median, standard deviation, minimum and maximum) of the score at each point in time as well as the percentage change to baseline Percentage of patients with PP NRS ≤1

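### SAP 8.2.3 row 11 is labelled absolute IGA change from baseline but specifies a summary and subgroup test of the raw score, and the SAP never defines the numeric difference

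*SAP*

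**What the plan says.** Protocol 9.1.1 gives two distinct endpoints under the physician's assessment: "e. Percentage change of IGA compared to baseline" and "i. Absolute change of IGA compared to baseline". The objectives in SAP 1.3 also name "IGA change to baseline".

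In SAP 8.2.3, the row with objective number 11 carries the absolute-change label: "Absolute change of IGA FAS, mFAS, PP All Summary statistics (n, None Excluded compared to baseline" (label, analysis sets and the start of the method cell run together in the text). The rest of the method cell reads "minimum and 11 maximum) of the score at each point in time Mann-Whitney-U test for subgroups", where the 11 is the row number. Row 9, which covers absolute EASI values over time, has the same method wording: "maximum) of the score at each point in time".

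For IGA, SAP 6.1 defines the responder rates, including IGA 0 or 1 combined with a reduction of at least 2 points. It also defines the score at each time point and the percentage change, with the formula "score at respective visit – score at baseline)/score at baseline*100" (opening bracket omitted). SAP 8.2.2 only points back to 6.1 and 6.3. Appendix 1 derives percentage change to baseline and has no entry for absolute change.

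**The concern.** The label and the method of row 11 describe different quantities. The method wording fits row 9, where the endpoint is the raw value. In row 11 the endpoint is a difference from baseline, and no other part of the SAP supplies that difference as a variable to be summarised.

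Two things are at stake. A secondary endpoint named in the protocol may go unreported, or may appear under its own title with the wrong content. And the subgroup test in that row would compare disease level at a visit, not improvement. SAP 8.2.3 uses no covariates, so nothing removes baseline severity from the comparison. Subgroups formed by dose sequence or medication history could plausibly differ in baseline IGA, and a table headed absolute change would then show a difference that is partly or wholly present before treatment.

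**Working it through.** The plan states no figure for this endpoint, so there is none to reproduce. The check is a comparison of the sections, followed by arithmetic on the 0-to-4 IGA scale.

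**1. Where could absolute change be defined?**
- SAP 6.1, IGA row: responder rates, score, percentage change. No stand-alone difference.
- SAP 8.2.2: cross-reference only.
- SAP 8.2.3, row 11: label is a change, method is the score.
- SAP 8.2.3, row 7: percentage formula.
- SAP 8.2.3, row 6: IGA 0/1 with a reduction of at least 2 points, a yes/no outcome.
- SAP Appendix 1: percentage formula.

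The undivided difference is used implicitly in row 6 and in the percentage numerator, but is nowhere named as a quantity to summarise.

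**2. Are the three quantities interchangeable?** Absolute change = visit − baseline; percentage change = (visit − baseline)/baseline × 100.

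| Baseline → visit | Raw score at visit | Absolute change | Percentage change |
|---|---|---|---|
| 4 → 2 | 2 | −2 | −2/4 = −50% |
| 3 → 1 | 1 | −2 | −2/3 = −66.7% |
| 2 → 1 | 1 | −1 | −1/2 = −50% |
| 4 → 3 | 3 | −1 | −1/4 = −25% |

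The first two rows share an absolute change but differ on the other two measures. The second and third share a raw score but not a change. Neither the score nor the percentage can stand in for the difference.

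**3. What does the raw score do to a subgroup comparison?** Let subgroups A and B have baseline means bA and bB and the same mean drop d. On the raw score the gap is (bA − d) − (bB − d) = bA − bB. On change it is (−d) − (−d) = 0. The documents give no baseline IGA by subgroup, so the inputs are assumptions:
- equal baselines: gap 0;
- 3.5 and 3.0, d = 1.5: 2.0 − 1.5 = 0.5;
- 4 and 3, d = 2: 2 − 1 = 1.

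The gap is always the baseline difference, whatever the drop.

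**4. Effect on the Mann-Whitney-U test (illustrative simulation).** Assumptions: 100 patients per subgroup; baseline IGA 4 in 70% versus 30%, otherwise 3 (means 3.7 and 3.3, gap 0.4); improvement of 0, 1, 2 or 3 points with probabilities 0.2, 0.3, 0.3 and 0.2 in both subgroups; two-sided 0.05; 4,000 runs. The test rejected in 5.4% of runs on absolute change, 18.7% on percentage change and 66.1% on the raw score. With no baseline difference the raw-score distributions would be identical and the rate would return to about the nominal level, so 66.1% is specific to this split.

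**5. Can a reader recover the change from the reported scores?** Not reliably. Example: baselines 4, 4, 4, 3, 3, 3; visit scores missing, missing, 2, 1, 1, 1. The difference of means is 5/4 − 21/6 = 1.25 − 3.50 = −2.25. The mean change in the four patients with both values is −8/4 = −2.00. The SAP excludes missing data, and its baseline rules (after the visit-window tables in 1.1) keep patients without a baseline in summaries but drop them from change analyses, so the denominators can differ.

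**The case against.** The row still names the endpoint as a change from baseline. A programmer could follow the label rather than the method cell, which looks like text carried over from row 9. The table shells are in a separate file (SAP 9) that is not available here and may show the correct derivation. A reader might infer that the endpoint will never be computed; the documents do not support that. They support only that label and method disagree and that no derivation settles the matter.

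It would also be wrong to infer that percentage change is the only form of IGA change left, or that the SAP nowhere subtracts baseline. Row 6 keeps a dichotomised point reduction, and the percentage formula contains the subtraction. Nor do the documents give grounds for demoting percentage change: it is the protocol's own endpoint (e).

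Protocol 9.7 lets the SAP modify the protocol's plans, so dropping the endpoint would be open to the sponsor. But the SAP declares no such change and keeps the endpoint's name.

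The consequence is modest. Subgroup tests are described as purely explorative, and baseline scores will be tabulated beside follow-up scores. For the two subgroup factors that are defined by response (EASI-90 responder and abrocitinib responder, the latter including IGA 0/1), an IGA comparison is partly circular on either measure. All of this stands. It limits the weight of the point without removing the contradiction.

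**Conclusion.** The point holds as a contradiction inside row 11 with no definition elsewhere to resolve it. Taken literally, the row summarises and tests the raw IGA score, so the numeric absolute-change endpoint of protocol 9.1.1 (i) is undefined in the SAP. The subgroup comparison would mix baseline severity with change, by an amount equal to the baseline difference between subgroups. How large that is cannot be read from the documents; the 0.5-point example and the 66.1% rejection rate rest entirely on assumed baselines. The endpoint is secondary and descriptive and no hypothesis is tested, so the exposure is one mislabelled or undelivered secondary result. The primary endpoints are not affected.

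**What to change.** - In SAP 6.1 (IGA secondary row) and Appendix 1, define absolute change of IGA as the score at the visit minus the score at baseline.
- In SAP 8.2.3 row 11, replace the method with summary statistics of that difference at each post-baseline visit, in patients with both values, and apply the Mann-Whitney-U test to the difference.
- Check that the table shells show the same quantity.
- Leave percentage change of IGA as the protocol specifies. A table of baseline against visit IGA category would be a useful addition, but is optional.

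The cost is a few lines of SAP text and one derived variable from data already collected. It should be done before database lock.
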